## 1.6 Study Rationale and Hypothesis

In summary, surgical resection is the only potentially curative treatment for patients with pancreatic cancer. Patients with BRPC have tumors in close contact with the vasculature but not to the extent that resection is prohibited. Nonetheless, retrospective studies have shown that immediate resection in these patients is associated with an increased risk of positive margins, and a margin positive resection does not improve survival over that of patients with unresectable disease. Moreover, even in those patients where a successful resection is achieved, there is a high rate of early metastatic progression suggesting that micrometastatic disease is often present at diagnosis. Therefore neoadjuvant therapy is likely to improve outcomes in patients with BRPC to increase the likelihood of achieving a margin negative resection, provide early control of occult micrometastatic disease, and select those patients without systemic progression who would benefit from surgical resection.

Superior survival outcomes have been demonstrated with FOLFIRINOX compared to gemcitabine in patients with metastatic disease. Our institutional prospective phase II trial demonstrated the tolerability and efficacy of modified FOLFIRINOX in patients with LAPC and MPC. Prolonged progression free survival and overall survival were seen in patients with BRPC and LAPC, and R0 resections were achieved in 42% of patients. In addition, retrospective and phase II studies have documented the tolerability of stereotactic body radiation therapy (SBRT) in LAPC and the potential for improved local control. Contact between the tumor and neighboring vasculature complicates or prohibits resection in the setting of BRPC, and therefore local therapy to potentially reduce the degree of contact may be of benefit. Given the superior outcomes with FOLFIRINOX and the potential for improved local response with SBRT, we propose to evaluate the efficacy of pre-operative modified FOLFIRINOX followed by SBRT in patients with borderline resectable pancreatic adenocarcinoma. We hypothesize that pre-operative modified FOLFIRINOX followed by SBRT will improve the rate of R0 resections compared to historical controls treated with standard gemcitabine-based chemotherapy and fractionated radiation prior to surgery.

## 2. OBJECTIVES

### 2.1 Primary Objective

To evaluate the R0 resection rate after neoadjuvant modified FOLFIRINOX and subsequent SBRT for borderline resectable pancreatic cancer.

### 2.2 Secondary Objectives

- 2.2.1 To evaluate the radiographic response to neoadjuvant therapy by comparing IV contrast CT scans before and after therapy.
- 2.2.2 To evaluate the pathologic response to neoadjuvant chemotherapy and stereotactic radiation.
- 2.2.3 To determine rates of recurrence (local only, systemic only, and both local and systemic), progression free survival, and overall survival.
- 2.2.4 To determine rates of grade 3 or greater gastrointestinal toxicity, including acute toxicities occurring within 3 months of treatment, and late toxicities occurring over 3 months after completion of radiation.

**2.3 Exploratory Objectives**

- 2.3.1 To prospectively assess quantitative *KRAS* mutation-associated circulating tumor DNA as a predictive marker of response to neoadjuvant therapy or a prognostic marker of outcomes.
- 2.3.2 To evaluate endoscopic ultrasound elastography measurements of tumor stiffness (change in strain ratio between the normal and tumor region before and after chemotherapy) as a predictor of outcomes.
- 2.3.3 To correlate response of CA19-9 to pre-operative therapy with outcomes.
- 2.3.4 To collect and bank serial serum and plasma specimens from subjects for future correlative biomarker studies.
- 2.3.5 To collect and bank tumor tissue from subjects prior to treatment (at the time of diagnostic EUS), after treatment with pre-operative FOLFIRINOX (at the time of fiducial placement for SBRT), and after SBRT (from the surgical specimen) for future correlative biomarker studies.

**3. STUDY DESIGN****3.1 Description of Study**

This is a Phase II open-label study to determine the efficacy of neoadjuvant mFOLFIRINOX followed by SBRT in patients with borderline resectable pancreatic adenocarcinoma. Patients will undergo a diagnostic endoscopic ultrasound (EUS) with core biopsy (or FNA if biopsy is attempted and unsuccessful) demonstrating pancreatic adenocarcinoma. Baseline elastography will be measured at the time of EUS, though patients will continue on study if elastography is not feasible. Borderline resectable disease will be defined by NCCN criteria, and determined centrally by review of a diagnostic pancreas protocol CT scan and/or MRI scan with contrast by a dedicated surgical oncologist and radiologist.

Patients will receive 8 cycles of mFOLFIRINOX every 2 weeks. mFOLFIRINOX will be dosed as follows: Oxaliplatin 85 mg/m^2, followed by folinic acid 400 mg/m^2 infused over 120 minutes and irinotecan 135 mg/m^2 infused over 90 minutes, followed by 5-fluorouracil 300 mg/m^2 IV bolus, followed by 2,400 mg/m^2 continuous infusion for 46 hours. Levoleucovorin may be substituted for folinic acid at a dose of 200 mg/m^2 infused over 120 minutes.

Patients will undergo a re-staging pancreas protocol CT scan after cycle 3 and after cycle 7. Patients without evidence of distant progression will continue on study. Patients will receive an additional 8th cycle of mFOLFIRINOX while radiation planning is underway. EUS will be performed for placement of fiducials to guide radiation delivery. Elastography will be performed and a core biopsy will be obtained at the time of EUS for correlative studies (patients will continue on study if elastography and core biopsy is not feasible). Stereotactic body radiotherapy (SBRT) will be delivered to the primary tumor and any adjacent involved nodes to 33 Gy in 5 fractions over the course of 2 weeks, and within 4 weeks of chemotherapy. All patients will be maintained on proton pump inhibitors beginning with the first SBRT treatment and continuing for at least 6 months after completion of SBRT, or at least until surgery if undergoing resection. After SBRT, patients will undergo re-evaluation with a pancreas protocol CT scan. Those patients who are resectable will undergo surgical resection between 4-12 weeks after completion of SBRT. Tissue from the resection will be banked for correlative studies. Post-operatively, patients will

receive 4 additional cycles of mFOLFIRINOX to complete a total of 12 cycles, with further dose modifications at the discretion of the treating medical oncologist.

Patients who complete the study treatment without disease progression will then enter a period of post-study surveillance which will include a history, physical exam, and laboratory assessments at three month intervals for three years and then 6 month intervals for two years, and CT scans at 6 month intervals for a total of three years, and then annually for an additional two years. After five years, patients will be followed annually until death.

### **3.2 Rationale for Study Design**

Recent advances in the treatment of pancreatic cancer include the use of FOLFIRINOX, which has been shown to significantly improve overall survival compared to gemcitabine in patients with metastatic disease, and the use of SBRT which may provide a therapeutic benefit with improved local tumor response compared to conventionally dosed radiation. The improved tolerability and comparable efficacy of a modified FOLFIRINOX regimen was demonstrated in our published institutional retrospective and phase II studies. Moreover, survival outcomes for patients with LAPC or BRPC treated with mFOLFIRINOX as part of the phase II trial were significantly prolonged compared to historical results with gemcitabine-based regimens. An ongoing phase II study at our institution is evaluating the efficacy of peri-operative mFOLFIRINOX for patients with resectable disease. Given the improved outcomes achieved with FOLFIRINOX and the retrospective and phase II data demonstrating tolerability and potential for enhanced local tumor response with SBRT, we propose an open label phase II study to evaluate the efficacy of neoadjuvant mFOLFIRINOX followed by SBRT in patients with borderline resectable pancreatic adenocarcinoma. We hypothesize that the addition of SBRT as part of pre-operative treatment will be associated with a significant improvement in the rate of R0 resections compared to historical controls receiving pre-operative standard gemcitabine-based chemotherapy and fractionated radiation.

### **3.3 Outcome Measures**

#### **3.3.1 Primary Outcome Measures**

The primary outcome of this study is the R0 resection rate in patients with BRPC treated with neoadjuvant mFOLFIRINOX and SBRT.

#### **3.3.2 Secondary Outcome Measures**

- 3.3.2.1** Radiographic response to neoadjuvant therapy
- 3.3.2.2** Pathologic response to neoadjuvant therapy
- 3.3.2.3** Local only, systemic only, and local or systemic rates of recurrence
- 3.3.2.4** Progression free survival
- 3.3.2.5** Overall survival
- 3.3.2.6** Grade 3 or greater acute and late gastrointestinal toxicity

### **3.4 Expected Accrual**

We expect to accrue 28 patients over approximately 56 months. Approximately 40 resections for pancreatic adenocarcinoma are performed annually at Yale New Haven Hospital, of which approximately one third are for BRPC. Therefore we anticipate enrolling approximately 6 patients per year.

## **4. ON-STUDY GUIDELINES AND SAFETY PLAN**

### **4.1 General On-Study Guidelines**

This clinical trial can fulfill its objectives only if patients appropriate for this trial are enrolled. All relevant medical and other considerations should be taken into account when deciding whether this protocol is appropriate for a particular patient. Physicians should consider the risks and benefits of any therapy, and therefore only enroll patients for whom this treatment is appropriate. Although they may not be considered as formal subject selection criteria, as part of this decision making process, physicians should recognize that the following may seriously increase the risk to the patient entering this protocol:

- Psychiatric illness that would prevent the patient from giving informed consent.
- Patient is not deemed a candidate for mFOLFIRINOX or SBRT based on overall condition and comorbidities.
- A medical condition such as active/uncontrolled infection or cardiac disease that would make this protocol unreasonably hazardous for the patient in the opinion of the treating physician.

### **4.2 mFOLFIRINOX-Specific Safety Guidelines**

Refer to section 7 for safety guidelines and recommendations for the management of toxicities related to FOLFIRINOX.

### **4.3 Radiation-Specific Safety Guidelines**

The radiation fractionation scheme proposed in this study (33 Gy in 5 fractions) was evaluated in a prospective multi-institutional phase II study in which patients with locally advanced pancreatic cancer received gemcitabine followed by SBRT. The rate of grade 3 or higher acute GI toxicity was 2% and the rate of grade 3 or higher late GI toxicity was 8%. Based upon this study and other published studies evaluating multi-fraction SBRT for pancreatic cancer, a rate of grade 3 GI toxicity of 20% or higher would be unexpected. An interim safety analysis will be performed by the PI after 5 patients complete 3 months of follow-up after SBRT. Study accrual will continue during this time period. If the rate of grade 3 GI toxicity that is probably related to SBRT exceeds 20%, then accrual will be held and the protocol and consent will be revised.

Refer to section 7 for recommendations for the management of toxicities related to SBRT.

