### Calendar of Assessments

Neoadjuvant mFOLFIRINOX:					
Tests & Observations	Screening			Day 1 of each cycle	Day 3, 4, or 5 of each cycle
	Within 14 days of starting study drug	Within 21 days of starting study drug	Within 42 days of starting study drug		
Scheduling Window (Days)				(±3)	(±3)
Surgical Evaluation			x		
History & Physical	x			x	
Height	x				
Weight/BSA	x			x	
Vital Signs	x			x	
Performance Status	x			x	
Toxicity Assessment	x			x	
Neulasta Q					x
Laboratory StudiesA:					
CBC, Diff, Platelets	x			x	
Serum Chemistries B	x			x	
PT/INR C	x				
CA 19-9, CEA	x				
Pregnancy Test D	x				
Research Blood Collection E	x				
Staging:					
CT (or MRI) F		x			
EUS (with elastography) G			x		
Neulasta					x
Tissue:					
Core Biopsy H			x		

Neoadjuvant SBRT and Pre-Operative Evaluation:			
Tests & Observations	Pre-SBRT (within 4 weeks prior to RT)	Weekly During SBRT	Pre-operative (within 4 weeks prior to surgery)
Surgical evaluation			x
History & Physical	x	x	
Weight/BSA	x	x	
Vital Signs	x	x	
Performance Status	x	x	
Toxicity Assessment		x	
Laboratory Studies:			
CBC, Diff, Platelets	x		x
Serum Chemistries B	x		x
PT/INR C			x
CA 19-9, CEA	x		x
Research Blood Collection E	x I	x J	x K
Staging:			
CT (or MRI) F	x		x K
EUS (fiducials and elastography) G	x		x L
Tissue:			
Core Biopsy H	x		

Adjuvant mFOLFIRINOX and Post-Treatment Follow-Up:					
Tests & Observations	Day 1 of 1 st adjuvant cycle (within 12 weeks of surgery)	Day 3, 4, or 5 of each cycle	Day 1 of each subsequent cycle	Post-Treatment Follow-Up N	30-day follow-up
Scheduling Window (Days)	(±3)	(±3)	(±3)	(± 14)	(± 7)
History	X		X	X	X
Physical Exam	X		X	X	X
Weight/BSA	X		X	X	X
Vital Signs	X		X		
Performance Status	X		X	X	
Toxicity Assessment	X		X		
Neulasta Q		X			
Laboratory StudiesA:					
CBC, Diff, Platelets	X		X	X	
Serum Chemistries B	X		X	X	
CA 19-9, CEA	X			X	
Research Blood Collection E	X			X O	
Staging:					
CT (or MRI) F				X P	X
Tissue:					

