## 10. SUBJECT DISCONTINUATION

Patients will receive 8 cycles of neoadjuvant mFOLFIRINOX followed by SBRT, surgical resection, and post-operative mFOLFIRINOX to complete 12 cycles. Treatment will continue unless there is evidence of disease progression, or unacceptable toxicity as specified in section 7.3 of the protocol. Any patients deemed unresectable at the time of surgery will be discontinued from study treatment.

Patients who complete the study treatment phase without disease progression will enter a post-study surveillance phase. They will undergo history, physical exam, measurement of weight, evaluation of performance status, and laboratory assessments (including CBC, serum chemistries, liver function tests, CA 19-9, CEA, and a research blood collection, as specified in the study calendar) at three month intervals for three years, then every six months for two years, then annually or until disease recurrence or death. Cross-sectional imaging with CT or MRI will be performed at 6 month intervals for three years, and then annually for two additional years or until disease recurrence. After five years, patients will be followed annually until death; surveillance imaging and lab assessments are optional after five years.

In addition, subjects who meet the following criteria should be discontinued from study treatment:

- Any grade 3 or 4 toxicity that does not resolve within 3 weeks of holding treatment.
- Unwillingness or inability of subject to comply with study requirements
- Determination by the investigator that it is no longer safe for the subject to continue therapy, or that the constraints of this protocol are detrimental to the patient's health
- The patient no longer wishes to continue protocol therapy

All subjects will be followed for survival.

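### Acute GI toxicity to 3 months after SBRT feeds an endpoint and the accrual hold, but for irradiated patients who are not resected routine capture stops about 30 days after SBRT

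*Combined protocol and SAP*

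**What the plan says.** **What needs the data.** Section 2.2 sets grade 3 or greater GI toxicity as a secondary objective and splits it into "acute toxicities occurring within 3 months of treatment, and late toxicities occurring over 3 months after completion of radiation". Section 3.3.2 lists it as an outcome: "Grade 3 or greater acute and late gastrointestinal toxicity". Section 4.3 adds the only numeric SBRT safety rule. The timing is "An interim safety analysis will be performed by the PI after 5 patients complete 3 months of follow-up after SBRT", accrual continues meanwhile, and the trigger is: "If the rate of grade 3 GI toxicity that is probably related to SBRT exceeds 20%, then accrual will be held".

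**What is scheduled.** In the SBRT and pre-operative table of the Section 8 calendar, the Toxicity Assessment row is marked only in the weekly column during SBRT. The pre-SBRT column has a history and physical but no toxicity mark. The pre-operative column has neither; it holds a surgical evaluation, laboratory tests, imaging and research blood. The next mark is day 1 of the first adjuvant cycle. The post-treatment, 30-day and long-term follow-up columns have no toxicity mark.

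**Who leaves.** Section 10: "Any patients deemed unresectable at the time of surgery will be discontinued from study treatment". Surveillance visits are written for patients who complete study treatment without progression. All subjects are followed for survival.

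**General safety provisions.** Section 13.1 asks for a toxicity-directed history at every visit. Section 6.4 provides medical oncology follow-up every 2 weeks after surgery. Section 14.2 captures new adverse events until 30 days after last treatment or withdrawal, unless otherwise specified. After that it records only unexpected serious events attributed to drug administration.

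**The concern.** The endpoint and the hold rule both need GI events through 3 months after SBRT. The calendar has no toxicity assessment tied to that period once SBRT ends, and no 3-month contact, although Section 4.3 names that time point. For patients who go on to surgery and adjuvant chemotherapy, other provisions fill much of the gap. For those who receive SBRT and are not resected, nothing in the documents clearly does.

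Two things are at stake. The acute rate can be biased low if events in the less-followed group go unrecorded. And a safety rule applied to 5 patients can fail to trigger because of a single unrecorded event.

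A smaller matter concerns attribution. Cycle 8 is given while SBRT is being planned, and the pre-SBRT visit may take place before its toxicity appears. Without a graded baseline between cycle 8 and the first fraction, it is harder to judge whether an early event is probably related to SBRT.

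**Working it through.** The plan gives no operating characteristics for the 5-patient rule, so there is no stated figure to reproduce. The Simon design figures in Section 12 do not bear on this point.

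**1. Capture window against endpoint window.** Three months is taken as 13 weeks, or 13 x 7 = 91 days. If SBRT is the last treatment, Section 14.2 captures new events to day 30. The open part is 91 - 30 = 61 days, and 61/91 = 67% of the acute window.

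**2. Interval between calendar-marked assessments in resected patients.** Surgery is 4 to 12 weeks after SBRT (Section 6.3) and adjuvant therapy starts within 12 weeks of surgery (Section 6.4).
- Shortest: just over 4 weeks after SBRT, inside the 3-month window.
- Longest within those limits: 12 + 12 = 24 weeks. Section 6.3 allows later surgery with PI approval.

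This is the interval between marked assessments, not between contacts. If the first post-operative visit falls about 2 weeks after surgery, it comes 4 + 2 = 6 to 12 + 2 = 14 weeks after SBRT.

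**3. Coverage by group.**

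| Group | To day 30 after SBRT | Day 30 to 3 months |
|---|---|---|
| Resected, goes on to adjuvant therapy | Event capture open | Event capture open; pre-operative contact and 2-weekly post-operative visits, with a toxicity history at each |
| Irradiated, not resected | Event capture open | At most a pre-operative evaluation, if one took place; routine capture closed if counted from SBRT; then survival follow-up |

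**4. The hold rule.** Exceeding 20% of 5 means more than 1 event, so at least 2. With X the recorded events and p the probability of a recorded event per patient:

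P(hold) = P(X >= 2) = 1 - (1-p)^5 - 5p(1-p)^4.

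Section 4.3 cites grade 3 or higher GI rates of 2% (acute) and 8% (late) from the earlier multi-institutional trial. With complete recording, P(hold) is 0.004 at 2% and 0.054 at 8%. At the 20% threshold it is 1 - 0.8^5 - 5(0.2)(0.8^4) = 1 - 0.328 - 0.410 = 0.26.

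To show the effect of incomplete recording, p is replaced by p x s, where s is the share of true events recorded. The documents give no value for s. The shares below, and the 30% and 40% rates, are assumptions for illustration.

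| True rate | s = 1 | s = 0.75 | s = 0.5 | s = 0.25 |
|---|---|---|---|---|
| 20% | 0.26 | 0.16 | 0.08 | 0.02 |
| 30% | 0.47 | 0.31 | 0.16 | 0.05 |
| 40% | 0.66 | 0.47 | 0.26 | 0.08 |

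**5. When one unrecorded event matters.** It changes the decision only if exactly two occurred, turning 2/5 = 40% into 1/5 = 20%, which does not exceed 20%. P(exactly 2 of 5) = 10p^2(1-p)^3. At 20% this is 10(0.04)(0.512) = 0.20, most of the 0.26 chance of a hold. At 40% it is 10(0.16)(0.216) = 0.35 of the 0.66.

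**The case against.** The strongest reply is that the calendar is not the only instrument. Section 13.1 attaches a toxicity history to every visit, so the pre-SBRT history and physical and the pre-operative surgical evaluation are occasions to record events even without a mark. After surgery there are 2-weekly oncology visits, then marked assessments on day 1 of each adjuvant cycle. For patients who reach adjuvant therapy, event capture runs through the whole 3 months. Sections 13.1 and 14.2 allow a longer period if specified, and the 3-month definitions could be read as that specification. Section 14.2 also counts from withdrawal, which might extend capture for a patient found unresectable late. The PI reviews events regularly, and the DSMC reviews safety after 10 enrolments.

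Much of this stands for resected patients. A reader might infer from the calendar that toxicity is assessed only in the SBRT weeks, or that no later visit exists at which it could be recorded. The documents do not support either reading. Nor is 24 weeks a period without contact.

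The reply does not reach irradiated patients who are not resected. They have no post-operative or adjuvant visits, and neither safety section states a longer period for SBRT. Whether the 30 days run from SBRT or from withdrawal is left open. Section 13.1's extension until acute toxicities resolve follows events already known; it does not find new ones. After 30 days, the serious-event provision is limited to unexpected events attributed to drug administration and does not name radiation. The DSMC review is timed by enrolment, not by SBRT follow-up, and would rely on the same records.

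It is also fair that at the cited 2% acute rate the rule would almost never trigger. But the rule exists for the case where the true rate is much higher.

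**Conclusion.** The concern holds for irradiated patients who are not resected. For them, about 61 of the 91 days of the acute window can fall outside routine adverse event capture, with no scheduled toxicity contact to replace it. For resected patients the gap is partial: no marked assessment from the last SBRT week to adjuvant day 1, with other provisions covering much of the interval. The gap should be closed because it touches both an endpoint and the only numeric SBRT safety rule.

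The conclusion rests on three readings: the acute window runs 3 months from the end of SBRT; the 30 days in Section 14.2 count from SBRT when it is the last treatment; and nothing else in the plan specifies a longer period.

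Three stronger conclusions are tempting but not supported:
- That events will be missed or misattributed. This is a risk, not a certainty. Missed events would push the acute rate down, while chemotherapy effects attributed to SBRT would push it up, so only the effect of non-recording has a clear direction.
- That the number affected can be read from the planned R0 rates. Patients without an R0 resection include some who stop before SBRT and some resected with positive margins, so the number irradiated but not resected cannot be derived.
- That the loss of sensitivity in the table is what this trial would see. The shares are assumed and applied to all five patients, whereas the gap is concentrated in those not resected.

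**What to change.** 1. In the Section 8 calendar, mark Toxicity Assessment in the pre-operative column. Mark it also in the pre-SBRT column, as a graded baseline after cycle 8 and before the first fraction.
2. Add one toxicity contact at 3 months after the last SBRT fraction for every irradiated patient, resected or not. Telephone is acceptable.
3. Amend Sections 13.1 and 14.2 so that capture of GI adverse events runs to at least 3 months after SBRT, whether or not the patient remains on study treatment.
4. State in Section 4.3 that the interim safety analysis uses these assessments.

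The cost is a protocol and calendar amendment. The two marks fall at visits that already exist; the added burden is one contact per irradiated patient and a longer reporting period for those whose last treatment is SBRT. The change concerns data collection only and leaves treatment and the hold threshold as they are.

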Secondary endpoints include radiographic response to neoadjuvant therapy, pathologic response to neoadjuvant therapy, rates of recurrence (local only, systemic only, and both local and systemic), progression free survival, overall survival, and rates of grade 3 or greater acute and late gastrointestinal toxicity. We will compare levels of KRAS mutation-associated circulating tumor DNA, CA19-9, and elastography measures with outcomes including R0 resection using logistic regression, and progression free survival and overall survival using proportional hazards regression. We will code IV contrast scans as binary and compare the before/after treatment within the same subject using the McNemar test for matched pairs. We have not powered this study for these secondary and exploratory measures. Future correlative biomarker studies will be studied using standard bioinformatics methods. Progression free survival, and overall survival will be estimated using Kaplan-Meier analysis. The Cox proportional hazards regression model will be used to determine if survival outcomes are associated with patient characteristics or treatment-related toxicities.

We anticipate accrual will be completed in two years based on the fact that approximately 40 resections for pancreatic adenocarcinoma are performed annually at Yale New Haven Hospital, of which around a third are for BRPC.

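### Read literally, the SBRT accrual-hold rule counts grade 3 GI events only, while the rates behind it and the trial's GI endpoint take in grade 3 and above

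*Combined protocol and SAP*

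**What the plan says.** Section 4.3 starts from an earlier multi-institutional phase II study of the same fractionation. It reports that "The rate of grade 3 or higher acute GI toxicity was 2" percent and that "the rate of grade 3 or higher late GI toxicity was 8" percent. It then calls a grade 3 rate of 20% or more unexpected; there, the words allowing for more attach to the rate and not to the grade. The timing follows: "An interim safety analysis will be performed by the PI after 5 patients complete 3 months of follow-up after SBRT". The trigger is: "If the rate of grade 3 GI toxicity that is probably related to SBRT exceeds 20%, then accrual will be held". The protocol and consent would then be revised.

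The trial's gastrointestinal endpoint appears in three places, each covering grade 3 and above:

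- Section 2.2: "To determine rates of grade 3 or greater gastrointestinal toxicity", with acute events defined as "acute toxicities occurring within 3 months of treatment".
- Section 3.3.2: "Grade 3 or greater acute and late gastrointestinal toxicity".
- Section 12: "rates of grade 3 or greater acute and late gastrointestinal toxicity".

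Section 13.4 lists five attribution categories, with Probable and Definite as separate entries.

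**The concern.** The hold sentence and the material around it describe different sets of events. The evidence and the endpoint cover grades 3, 4 and 5; the trigger names grade 3. Elsewhere the protocol usually writes the range out when it means more than one grade: Section 7.3.7 refers to grades 3-4, and Section 10 to grade 3 or 4.

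This is the only study-level numeric toxicity trigger in the plan; the thresholds in Section 7.3 apply to individual patients. If the sentence is followed as written, a more severe event can fail to count where a less severe one would. The principal investigator, who performs the analysis, would then have to settle the meaning with the results already in hand.

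The attribution wording raises a smaller question of the same kind. An event judged definitely related to SBRT is not named in the sentence, and the protocol's own scale separates Definite from Probable.

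**Working it through.** The plan states no operating characteristic for this rule, so there is no figure to reproduce. The check has three parts.

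**1. The wording, side by side**

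| Place | Grade | Attribution |
|---|---|---|
| 4.3, cited rates (2% acute, 8% late) | 3 or higher | not stated |
| 4.3, benchmark sentence | 3 | not stated |
| 4.3, hold sentence | 3 | probably related to SBRT |
| 2.2, 3.3.2 and 12, endpoint | 3 or greater | none |

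The grade differs between the hold sentence and both the cited rates and the endpoint. Attribution cannot be compared with the cited rates, because Section 4.3 gives none for them.

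**2. What the rule needs at five patients**

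Inputs from Section 4.3: n = 5, and hold if the rate exceeds 20%. I take the rate as patients with a counted event divided by 5.

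- 1/5 = 20%, which does not exceed 20%: no hold.
- 2/5 = 40%, which does: hold.

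So the rule is at least 2 of 5, and the classification of a single patient can decide it. Assume that every event below is judged probably related:

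| Events among 5 patients | Literal count | Count with higher grades |
|---|---|---|
| One grade 3, one grade 4 | 1/5, no hold | 2/5, hold |
| Two grade 4 | 0/5, no hold | 2/5, hold |

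These results need no assumed event rate.

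**3. What wider counting costs in unnecessary holds**

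For a true rate p of counted events, P(hold) = P(X ≥ 2) = 1 − (1 − p)^5 − 5p(1 − p)^4.

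- p = 0.02 (cited acute rate): 1 − 0.9039 − 0.0922 = 0.0038, or 0.4%.
- p = 0.08 (cited late rate): 1 − 0.6591 − 0.2866 = 0.0544, or 5.4%.
- p = 0.10 (2% + 8%, if acute and late events fell in different patients and all were visible at the look): 1 − 0.5905 − 0.3281 = 0.0815, or 8.1% (0.08146 before rounding).
- p = 0.20 (the threshold itself): 1 − 0.3277 − 0.4096 = 0.2627, or 26.3%.

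The look comes three months after SBRT and Section 2.2 places late events beyond three months, so the 2% case is the closest benchmark and the 10% case is deliberately unfavourable. Both assume that the cited rates carry over to this trial, where the chemotherapy before SBRT is different.

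**The case against.** The best answer is that the sentence is shorthand. Section 4.3 moves from rates for grade 3 or higher to a benchmark, expressly based on those data, that says only grade 3. The hold sentence then repeats the benchmark's grade and its 20%. A rule that held accrual for grade 3 events but not for a treatment-related death would be odd, and the authors very likely did not intend it. This stands as the likelier intention. It does not remove the gap, because no section defines the shorthand.

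On attribution the objection is stronger. In ordinary English, probably related sets a minimum. Section 4.3 does not refer to the scale in Section 13.4, whose categories are worded for investigational agents. The lists of possible, probable and definite in Sections 14.1 and 14.2 concern drug administration and reach down to possible, so they say little about whether Section 4.3 excludes definite. A reader might also infer that the attribution filter makes the trigger narrower than the 2% and 8% rates; the documents do not support that, because those rates carry no stated attribution. Nor is it inconsistent for a safety trigger to have an attribution filter while a descriptive endpoint has none. What remains is a request for clearer wording.

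Third, the plan has other protections. Section 11 lets the principal investigator terminate the study. Section 14.1 requires reporting of anticipated events that are more frequent than expected. Section 15 suspends enrolment at 10 patients until the DSMC approves continuing, and allows the principal investigator or the DSMC to suspend the protocol over a pattern in the incidence or severity of toxicity, with no attribution filter. These are real and they lower the severity. None of them defines what the numeric rule counts, and Section 15 gives no gastrointestinal threshold.

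**Conclusion.** The point holds on grade. Read literally, the hold sentence leaves out grade 4 and 5 events that the cited rates and the endpoint include, and at five patients one such omission can turn a hold into no hold. On attribution it is a wording point only: the sentence should show whether definitely related events count.

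Severity is low. The shorthand reading is probable, and Sections 11 and 15 give other routes to stopping or suspending the study. Two stronger inferences should be resisted. The first is that the trial would ignore grade 4 or 5 events; it would not, since they only fall outside the literal numeric trigger. The second is that a definite amount of detection is lost; the documents do not say what share of relevant events would go uncounted, and if the count is made on the shorthand reading the loss from the grade wording is zero.

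The conclusion rests on the literal text and on taking the rate as affected patients out of five. Only the false-hold figures depend on the cited rates applying here.

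**What to change.** Reconcile the grade wording of the hold sentence in Section 4.3 with the cited rates in that section and with the endpoint in Sections 2.2, 3.3.2 and 12. State explicitly which attribution categories count, with reference to Section 13.4. The aim is that more severe or more clearly related events are not left out of the count. The benchmark sentence should be aligned in the same amendment. As an optional clarification, and not because it is an error, the threshold could also be written as a count: 2 or more of 5.

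The 20% threshold, the timing of the look and the sample size stay as they are. The cost is a short amendment to Section 4.3, plus the small chance of an unnecessary hold: 0.4% on the closest benchmark and 8.1% in the unfavourable case. If the authors always meant the wider count, the amendment only records that.
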